## **C. Risks to Participants and Procedures to Protect Against Risk**

### **C.1 Adequacy of Protections against Risk**

We will make every attempt to minimize risks to participants throughout the study protocol, including loss of confidentiality or privacy and psychological discomfort.

#### **C.1.1 Recruitment and Informed Consent Procedures**

**Recruitment.** All participants will be recruited via geographically focused advertisements placed on MSM-oriented “hookup” mobile applications (e.g., Grindr, Scruff). These advertisements appear as ‘pop-ups’ within the apps when users log in within a specified radius of a given metro area. If users click on a ‘More Info’ button within these ads, they are directed to a ‘landing page’ for the eTEST study, which represents the first portion of the web app’s user-side onboarding process. After selecting their desired language (English/Spanish), a sequence of screens will explain the study in very simple terms. Then, basic eligibility criteria will be assessed using a series of online forms (see Section 3.C.3.4.). “Ballot stuffing” prevention

measures will be deployed to ensure that participants do not complete the eligibility assessment multiple times (e.g., barring multiple entries from the same IP or device MAC address).

Eligibility data will be discarded if participants do not meet criteria, and an error message will display notifying users that they are not eligible. Those who are eligible based on this data will be directed to create a user account in the web app before being directed to informed consent screens.

**Informed Consent.** On the first informed consent screen, participants will be able to elect to either read (written), hear (audio), or watch (video) a plain-language explanation of all information included in the consent process. Consent information will be explained/written at a sixth-grade reading level and important concepts will be highlighted via bulleted text, highlighted text, and/or captions. Participants will be required to type their initials next to each key concept presented to ensure that they have seen and understand each, as well as to indicate their overall consent. A short, three question ‘quiz’ will assess whether participants understand what is being asked of them. Those that get less than three correct will be returned to complete the informed consent section again. Those who enter correct answers to these questions will move on to complete the study baseline questionnaire. Afterward, those assigned to the eTEST condition will be directed to download the app from the app store specific to their OS (i.e., Android/iPhone).

Research staff and study test counselors will receive notifications, both via the administrator-side of the web app and via email, that a participant has completed their “onboarding” sequence. Staff will then conduct an introductory call with each participant. This call is designed to further emphasize the key points made by during the informed consent process, verbally assess participants’ understanding of the concepts, confirm contact information, and to stress the importance of adherence to the study. These calls will last approximately 10 minutes. Based on this conversation, if staff/counselors have reason to believe that a participant is not aware of study requirements and/or may be unable to provide informed consent, he/she will notify the participant that they are ineligible. If staff/counselors believe the participant understands and can provide consent, they will be formally considered “enrolled” after all other information is checked and verified.

**Payments.** Participants will be compensated on the basis on their completion of quarterly assessments, as well as the follow-up appointment conducted at the study’s end. They will earn \$25 for the baseline survey and each of the five quarterly assessments they complete, with a \$50 bonus for completing all assigned surveys within a week of their assignment. They will also earn an additional \$50 for completing the in-person HIV test after the study is finished, for a total of \$250. Participants will be paid for each survey immediately after completing it using a reloadable debit card that will be sent to each participant after enrolling. Study payments will be managed using the shared study database and issued by staff at Brown University. We successfully used this system, as well as a similar compensation schedule, in our pilot study (see Section 3.A.5.). Compensation amounts are consistent with payments provided for research participation at Brown and other institutions, thus posing little risk of coercion.

## C.2 Procedures to Protect Against Risk

**C.2.1. Protections against the loss of data security, confidentiality, and privacy.** Before beginning their work on the study, all members of the research staff will receive thorough training in procedures designed to maintain data security. Informed consent procedures have been specifically designed to ensure that participants are aware of the study's potential risks to confidentiality and privacy. We have elected to conduct this consent process entirely online, because we believe that the eTEST system may be most appealing and beneficial for those MSM who may have been deterred from testing because of the face-to-face interaction that is normally required. However, the online informed consent process is thorough, and involves several steps designed to ensure that participants understand its key components, including: presenting key concepts in several formats (written, audio, video), condensing presented material to key points, requiring that participants initial each key point, and requiring that participants complete a short quiz to demonstrate their understanding. RAs will also call participants on the phone to verify their understanding of study procedures before considering them 'enrolled.' While some may have reservations about conducting and collecting informed consent online, we believe doing so offers participants a better opportunity to consider their participation in private and freely decline participation, if they so choose. We also believe that these steps for ensuring participants' informed consent also actually exceed of those undertaken in many in-person consent procedures.

*(1) Data security.* While collecting and storing participants' personal information using web-connected databases is unavoidable due to the nature of the study, a number of steps will be used to help secure and safeguard this data throughout the project. All elements of the proposed web architecture (web application, mobile application, database) will be hosted on Brown University's secure internal servers. Hosting these elements locally has the benefit of allowing us to enforce a strict set of security and authentication rules and exercise more control over who has access to the data (i.e., to only essential research staff, and information technology staff directly involved in maintenance and oversight of the server). We can also require additional security measures for all authorized individuals, such as two-step verification (a password plus registered device), VPN-only access, and IP-specific firewall rules. Access to participant information will be restricted to essential research staff, and only after two-step verification. Given the sensitivity of some of the data collected as part of this project, servers running elements of the eTEST architecture will conform to 'restricted-level' server settings. In addition to more stringent virtual access controls, this designation also means more stringent physical access controls, and that Brown's Computing and Information Services (CIS) staff performs continuous monitoring, emergency support/backup, and regular penetration tests. More details about server security designations at Brown is available at: <http://brown.edu/go/serversecurity>.

Questionnaire data collected throughout the study will also adhere to similar server/data security measures, since these elements are also hosted on the same internal servers. Specifically, these surveys will be developed and hosted using Qualtrics, which allows researchers to create individualized surveys and host them on local servers, to ensure local control over security settings and access policies. By using Qualtrics, we can send online surveys to research participants that they complete on web applications hosted at Brown. These surveys can also be mobile-optimized, so that participants can easily complete them on their mobile devices.

*(2) Privacy when using mobile/online tools and assessments.* Since participants will complete quarterly questionnaires online, and some questions asked will be sensitive, they will be specifically instructed to complete these in a private location when possible. Emails that are automatically sent to participants to remind them to complete the surveys will also remind them

to complete assessments in private. Reminder emails will also contain no identifying information (other than their email address) or references to HIV testing or other sensitive topics.

All participants will have access to information about HIV and other sexually transmitted infections, testing, prevention, and referral information via the eTEST app. As such, they will be instructed to use their phone's lock screen to prevent unauthorized access. They will also be instructed to access this information only in private locations. Users will receive push notifications from the app, either to inform them that they are due for their next test, or to inform them about the status of their next HBST kit (i.e., that it has been shipped, that it has been opened and a counselor will be reaching out soon). These notifications will be worded as innocuously as possible (e.g., "Looks like you opened your test!"), and test opening notifications in particular only register when the device is in close proximity to the beacon ( $\approx 50\text{m}$ ), ensuring that they display only when participants are already in a location in which they are comfortable taking the HIV test. Still participants will be encouraged to use their devices' native security settings (e.g., enabling a lock screen with code in order to access the phone) while they are in the study. No participants have expressed concerns about the privacy of the app in our pilot study. The Bluetooth low energy (BLE) beacons used in test kits do not collect or store any data. They only transmit information about the beacon and its state to nearby Bluetooth devices (e.g., smartphones).

(3) *HBST Packaging.* If participants have been assigned to either the standard HBST or eTEST conditions, OraSure OraQuick® HBST kits will be sent to the verified physical addresses of participants throughout the study. To safeguard participant confidentiality, these packages will be sent with generic return addresses (i.e., Brown University) and in discrete packaging. An information card will also provide participants with tips for ensuring their privacy while taking the test at home and for disposing of the test collection swab. OraSure provides an envelope container that participants can use to confidentially dispose of the test collection swab after the test is complete.

(4) *Phone counseling/follow-up interviews.* When conducting follow-up phone calls, counselors will first ensure that participants have adequate privacy to discuss the test over the phone, and if not, calls will be re-scheduled. Data from these calls will be manually entered by counselors into the study's central, password-protected database. Occasionally, counseling phone calls will also be digitally recorded for training, supervision, and fidelity purposes. These recording files will be password-protected and stored on Brown University's secure servers, in locations separate from participants' identifying data. Digital audio recordings collected for supervision purposes will be deleted immediately after supervision meetings have occurred. Those used for training and fidelity will be stripped of any identifying information that may have been recorded, and deleted after they have been used for these purposes.

**C.2.2. Protections against psychological discomfort/distress.** Several measures will also be employed to minimize psychological discomfort or distress as a result of the research. First, while participants may experience some nervousness or anxiety while taking an HIV test at home, past research suggests that this risk is low 159-161, and OraSure's clinical trial data suggests that HBST can be completed safely and with minimal distress. Nevertheless, participants in either HBST condition (standard HBST, eTEST) will be encouraged to report any distress they experience as a result of testing to study staff, who will provide referral to LGBT-friendly treatment providers in the local area. Second, some participants may receive "reactive" results during the study, so this possibility will be addressed during their "onboarding" and consent process. This sequence will explicitly encourage participants to interpret HBST test

results as “reactive” (rather than “positive”), since false-positive results are possible and further testing is needed to confirm “positive” results. Participants in any condition will also be encouraged to report receiving “reactive” results to study counselors as soon as possible, and will be provided with contact information for doing so. When reporting a “reactive” result, study test counselors will aid these participants in scheduling an appointment for confirmatory testing at clinics specific to their areas and at which site PIs have existing relationships (see Section A.2. for a list of these and other referral sites). Each of these clinics have established procedures for conducting follow-up testing and engaging these patients in ongoing HIV care. Finally, the risk of distress or discomfort from study assessments is low, but participants will again be encouraged to report this to study staff as soon as possible. Staff will then provide referrals to local MSM-friendly treatment resources and/or emergency services. In addition, research staff will be trained in responding to adverse events, including participant distress. These events will be reported promptly to the Brown University IRB and the IRBs of the relevant site. Together, we believe that these procedures greatly reduce any risks associated with the research, both in terms of data security and possible emotional discomfort/distress.

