### **Clinic records.**

We will also review clinical data for each participant to compare with self-report data on HIV testing, STI testing, and PrEP uptake. We will obtain a signed HIPAA release to review the records of area clinics where participants reported receiving these services. Data on verified service use will be compared across conditions to explore potential differences. While we realize that this data may be incomplete (especially given that some may elect to test at certain sites anonymously), we believe that collecting as much corroborating data as possible will serve as an important compliment to self-report data. Data collected is limited to:

- Date of HIV test
- Viral load
- CD4 cell count
- Type of HIV test (blood vs. antibody)
- HIV status
- Whether the patient received counseling to reduce their risk for HIV
- Date of each STD test
- STD tested
- Test results
- Whether the patient spoke to a provider about PrEP
- Whether the patient was prescribed PrEP

\*Data Use Agreements will be put in place to allow staff at each study site access to the study database (saved on Brown's servers) in order to verify service use and enter data collected.

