Once users have registered, staff will conduct a brief introductory call with all participants to ensure that their information is correct and that they understand the study's requirements. After successfully completing this call, study staff will mark these participants as 'fully enrolled,' activating them in the study database. For **control** group participants, test messages will be sent to remind users when they are due to test. Tests will include a link to a web service listing nearby clinics offering HIV testing, as well as their location, phone number, hours, and cost. For **standard** HBST group participants, staff will send an HBST kit to their confirmed shipping addresses. These participants will receive no phone-based follow-up, but can use OraSure's provided 1-800 number for questions or needs. We will follow the same steps for **eTEST** participants, except that each test kit will be fit with an Estimote™ beacon. Beacons will automatically detect when each kit is opened and relay this information to a central study database, which triggers an email notification sent to counselors. Within 24 hours of opening the kit, an HIV test counselor will call **eTEST** participants to conduct post-test counseling and refer them to other needed services, including PrEP (see Section 3C.3.6.1.). HIV test counselors will be bachelor's-level staff who are certified as HIV test counselors and will have crisis intervention training. Clinical assessment and analysis of mental health will remain a responsibility of the licensed study clinician. At least one HIV test counselor will also be fluent in Spanish. Counselors will record data during each call in the study database. In each condition, participants will receive these interventions every three months over the course of the study period: at baseline, 3, 6, and 9 months.

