Online surveys will use Qualtrics and will be hosted on Brown University servers. On each quarterly survey's due date, the study database will automatically send participants an email with language-specific instructions and links to the surveys. Participants will be asked to complete these within two days, and reminder emails will be sent every other day for seven days after the due date. If participants have not completed the survey within a week of their due date, site-specific RAs will contact participants by phone, text message, and email to encourage adherence. For all participants, those who fail to complete two consecutive quarterly assessments will be considered to have withdrawn from the study. After participants complete their final online survey, they will be asked to present to designated clinics for in-person HIV testing to finish the study. Site RAs will conduct follow-up calls with participants to ensure adherence to this procedure. Study payments will be issued via a reloadable debit card that will be mailed after participants are activated in the study. Participants will earn \$25 for the baseline survey and each of the five quarterly surveys they complete, with a \$50 bonus for completing all within a week of their assignment. They will also earn an additional \$50 for completing the in-person HIV test after the study is finished, for a possible total of \$250.

Focused information/counseling on PrEP. PrEP education and counseling will take place at each post-test phone call with participants in the **eTEST** condition. During the first call, HIV test counselors will provide a brief PrEP education session, covering indications for PrEP eligibility, a description of the medication used for PrEP, and an overview of common side effects and clinical follow-up (every three months). In our past work, we have employed an effective, five minute PrEP education session during in-person HIV testing that resulted in greater PrEP awareness among MSM131, and this will guide the education delivered during HIV test counselor phone contacts. Following the education content, participants will be asked whether they are interested in making an appointment with a medical provider for PrEP consultation.

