## Planned Analyses

Analyses will be conducted in Year 5. To evaluate Aim 1(a), we will use factorial logistic regression to test whether rates of having completed any HIV test over the 12 month study period (assessed via self-report and/or clinic records) differ by study condition. Condition, study site (and their interaction) and other relevant covariates will be entered as predictors, allowing us to explore whether each condition's effects differ by study site. To explore the effects of study condition on regular HIV testing, we will use a generalized estimating equation (GEE) for repeated, binary outcomes, specifying whether participants tested during each 3-month study period as the focal outcome. A logit link function and independent correlation structure will be specified, with study condition, site, and relevant covariates as predictors, to test whether the odds of testing differ across time period, condition, and site. GEEs are a fitting approach for studies in which correlations between repeated measures variables are to be controlled, rather than a central focus of the analysis. For all models of **HIV testing** outcomes, a covariate reflecting whether a given participant had initiated PrEP (and when, for longitudinal models) will be added to each model, since these individuals are required to test for HIV quarterly as a part of ongoing PrEP care. Doing so will allow us to estimate the effects of study arm on HIV testing among those who did not initiate PrEP. Given that we have proposed collecting 54 more participants per site (162 total) than is required to estimate our most complex model (see Model 1b in Section 3C.3.10), we believe we will be fully powered to test this model, even with a high rate of PrEP adoption. While contamination of the control group in our pilot study was rare (only one control participant reported using a HBST), we will also track **where** each participant tested (at home, in person) in quarterly surveys. If contamination is significant, we will employ methods aimed at reducing this bias, including adding indicators of contamination as covariates or bootstrapping. To evaluate Aim 1(b), we will generate variables reflecting whether participants received testing for other STIs or risk reduction counseling during each of the four 3-month intervals of the study period. Similar GEE models will be estimated for these outcomes with time period, condition, and site as predictors, to test whether the odds of receiving each service differ across these factors. To evaluate Aim 2, we will code variables indicating whether participant reports or clinic records reflect participants having consulted with a medical provider about PrEP and/or received a PrEP prescription any time across the study period. Factorial logistic regression with study site, condition, and their interaction will be entered as predictors of this outcome, to test whether the odds of having received consultation and/or a PrEP prescription differ across each of the study sites and conditions. Overall, data from those who drop out or withdraw from the study will be used in these analyses, in intent-to-treat (ITT) fashion. Similarly, we will assume values of zero for all outcomes (i.e., non-receipt of testing or services) when quarterly assessments are missing but participants are retained in the study. Depending on the degree of missing assessments, we will use multiple imputation for these values, since data from missing assessments will likely be missing not at random.

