identify for the purposes of verifying service receipt and collecting limited clinical data (e.g., HIV/STI test results, and if positive, CD4 counts and viral loads). Quarterly online surveys will ask participants to name the specific clinics where they received each of the services that the questionnaires inquire about, and site-specific RAs will then request records from these clinics for these participants. Site-specific RAs will download participant data to explore service utilization and compile lists of participants who noted receiving services at each clinic. RAs will then contact each clinic that a participant utilized for HIV/STD testing. Once clinic data is received, site-specific RAs will code it using participants' unique study ID numbers and store it in password-protected files on Brown University's secure servers.

We realize that not all services will be verifiable (e.g., anonymous HIV testing), and that some participants may not be comfortable signing broad releases for their medical information. We also acknowledge that requiring the release of personal medical data may serve as a barrier to enrolling for some participants. At the same time, we also believe it is important to collect more objective data that can serve as a compliment to self-report whenever possible. Given these considerations, returning a signed release will not be required in order to enroll in the study, to prevent this procedure from acting as an impediment to enrollment. Instead, we will verify clinical service information for those who return their releases and consent to this specific procedure. This approach will allow us to verify as much clinical service data as possible, while minimizing participant discomfort with the study's procedures. While this likely means that data on clinical service use will be incomplete, we do not believe that incorporating this procedure undermines the importance of self-report data or the study as a whole. (See Section B4 for a full list of data collected from clinics.)

\*Data Use Agreements will be put in place to allow staff at each study site access to the study database (saved on Brown's servers) in order to verify service use and enter data collected.

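### Late surveys are chased without a cap by site staff from whom the arm is not hidden, and zero-scoring turns any arm difference in survey completion into a false treatment difference

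*Combined protocol and SAP*

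**What the plan says.** **Access.** C.2.1, part (1) Data security, states: "Access to participant information will be restricted to essential research staff, and only after two-step verification". Clinic records (B.4), repeated in B.5.1.4, adds: "Data Use Agreements will be put in place to allow staff at each study site access to the study database", for checking service use and entering data. These rules work by role and authentication. No part of the protocol supplied mentions masking of staff or a database view restricted by arm.

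**What the database holds.** Procedure (B.4): "Beacons will automatically detect when each kit is opened and relay this information to a central study database". B.5.1.1 adds that counselors log their post-test calls through the web application's admin panel, and that all components share one central database. Both kinds of record arise only in the eTEST arm.

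**Who collects outcomes.** Procedure: automated emails come first; once a survey is a week late, "site-specific RAs will contact participants by phone, text message, and email to encourage adherence". The rule is worded alike for all arms but sets no maximum number of attempts and no contact log. In B.5.1.4 the site RAs download participant data, list participants by clinic, and "RAs will then contact each clinic that a participant utilized for HIV/STD testing". Site RAs also hold the end-of-study interview about the app and kits (Individual interviews).

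**Scoring.** Planned Analyses: "we will assume values of zero for all outcomes (i.e., non-receipt of testing or services) when quarterly assessments are missing", for participants still in the study. The next sentence allows multiple imputation instead, according to how much is missing, with no threshold.

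**The concern.** Participants cannot be masked to home kits or clinic reminders, but the effort spent on obtaining a late survey can be made independent of arm. As written, the effort is open-ended, and the staff who decide on it have access to a system containing arm-revealing data.

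That matters because of the scoring rule. A man who tested but did not return the survey is counted as a non-tester for that quarter, so anything that raises completion in one arm raises its apparent rate of HIV testing, STI testing, counseling and PrEP contact. Clinic records are only a partial backstop: the clinics are identified from the same surveys, the release is optional, and a home test leaves no clinic record. Uneven record requests could also move verified service use.

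**Working it through.** **The plan's own figures.** The plan gives no completion by arm, so there is no figure to reproduce on this point. Its sample-size surplus does reproduce (300 − 246 = 54 per site; 54 × 3 = 162), but extra participants do not reduce a bias. They make it more likely to reach significance.

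**Inputs**
- Four periods, correlation 0.2, alpha 0.05: Power Considerations. Two-sided testing is assumed.
- 667 per arm: 2000 / 3, assuming equal allocation. 300 per arm: 300 per site × 3 sites / 3 arms, from Power Considerations.
- Assumed: true testing rate p = 0.60 per quarter in both arms, so no true effect; completion 90% in one arm and 1 to 5 points higher in the other; every missed survey scored zero; missingness unrelated to testing.

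**Formulas**
- Observed rate = p × completion, so false difference = p × completion gap.
- Effective n per arm = 4n / (1 + 3 × 0.2) = 2.5n, which is 1,667.5 for n = 667 and 750 for n = 300.
- SE = √[a(1 − a)/n_eff + b(1 − b)/n_eff], where a and b are the observed rates; z = (b − a)/SE.
- False-positive rate = Φ(z − 1.96) + Φ(−z − 1.96).

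**One case in full** (3-point gap, 667 per arm): a = 0.60 × 0.90 = 0.540; b = 0.60 × 0.93 = 0.558; difference 0.018; SE = √(0.2484/1667.5 + 0.2466/1667.5) = 0.01723; z = 1.045; rate = Φ(−0.915) + Φ(−3.005) = 0.181.

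| Completion gap | False difference | False-positive rate, 667 per arm | 300 per arm |
|---|---|---|---|
| 0 | 0 | 5.0% | 5.0% |
| 1 point | 0.6 points | 6.4% | 5.6% |
| 2 points | 1.2 points | 10.7% | 7.5% |
| 3 points | 1.8 points | 18.1% | 10.8% |
| 5 points | 3.0 points | 41.5% | 21.5% |

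**Dependence on the testing rate.** With completion of 94% against 89% and testing rates of 0.5, 0.7 and 0.9, a pooled two-proportion test gives false differences of 2.5, 3.5 and 4.5 points. The false-positive rates are about 31%, 56% and 93% at 666 per arm, and 16%, 29% and 63% at 300.

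**Any test in 12 months.** A beta-binomial simulation (testing correlation 0.2; completion correlation 0.5, assumed), also with 94% against 89% and quarterly testing of 0.3 to 0.7, gives false differences of about 2.4 to 2.7 points. The false-positive rates are 16% to 36% at 666 per arm and 10% to 19% at 300. These are upper-end figures, because they allow no recovery of a missed test from a later survey or a clinic record.

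**The case against.** Several stronger readings are tempting, and the documents do not support them.

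- **That the RAs know the arm and chase unevenly.** Uneven chasing is nowhere described, and the rule is the same for all arms. That the RAs can see the arm is inferred from the access rules and database content. C.2.1 does say "RAs will also call participants on the phone to verify their understanding of study procedures before considering them" enrolled, but B.5 gives this call to research staff and C.1.1 to staff or counselors; no section says that the site RAs who chase surveys make it.
- **That a missed survey always counts as zero.** The rule covers retained participants only, and imputation may replace it. The missing trigger stands as a weakness: at low missingness zero-scoring could well remain in force. Two consecutive missed surveys count as withdrawal, and scoring after that is described only as intent-to-treat.
- **That the pilot's completion range (86% to 100%) shows gaps of this size.** That range is monthly and pooled over arms. With 73 men at 94%, chance alone gives an SD of √(0.94 × 0.06/73) = 2.8 points. It says nothing about differences between arms.
- **That equal chasing would remove the bias.** Only equal completion does. eTEST participants alone receive counselor calls (Procedure) and contact after deleting the app (B.5), so completion can differ under identical RA effort.

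The larger gaps would also need a marked difference in chasing. If 80% had answered before RAs step in (an assumption), final completion of 90% against 93% or 95% means converting 10/20 = 50% of the rest against 13/20 = 65% or 15/20 = 75%. Finally, outcomes draw on self-report and/or clinic records, and each survey asks about testing since the last assessment, so some missed tests would be recovered.

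These points reduce the likely size. They leave standing that effort is uncapped, the arm is not hidden, and the default scoring is sensitive to completion.

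**Conclusion.** The point holds as a worthwhile, inexpensive improvement in how outcomes are collected; it does not show that the trial is biased. While zero-scoring applies, the false difference is the testing rate times the completion gap. On the stated assumptions a 1- or 2-point gap does modest harm (6.4% and 10.7% at 667 per arm; 5.6% and 7.5% at 300), and 3 or 5 points does substantial harm (18.1% and 41.5%; 10.8% and 21.5%). The result rests on assumed gaps, an assumed 60% testing rate, equal allocation and no recovery of missed tests. With equal completion the bias in this calculation is zero.

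**What to change.** 1. In Procedure (B.4), set one contact schedule for late surveys in all arms: same channels, same maximum number of attempts, each attempt date-stamped.
2. In C.2.1, add that RAs who chase surveys work from a database view showing contact details and due dates, but not arm, app status or call logs.
3. Where feasible, request clinic records from a list without arm, and hold the end-of-study interview only after the participant's last outcome is closed.
4. Report survey completion and contact attempts by arm.
5. In Planned Analyses, run the multiple imputation as a sensitivity analysis alongside zero-scoring, whatever the amount missing. Masking cannot remove completion differences caused by eTEST-only contacts, so this step is needed in addition to the first two. The section itself expects data missing not at random, so imputation is a comparison, not a full correction.

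**Cost.** A restricted view in a database already custom-built, a contact script and log, and one further analysis. Arm-specific questions must pass to another team member, some participants will reveal their arm in conversation, and the survey extracts used for record requests may still show it. Reassigning the introductory calls and fully masking record coding would cost more, and the point does not depend on them.
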